- Correlation less than 0.95 between any two parameter estimates.

For the final PPK model, diagnostic plots will be presented.

The plasma maltol and maltol glucuronide concentration-time profile at steady state will be predicted using the PPK parameters estimates in the final model.

The pre-dose adjusted incremental $AUC_{(0-6h)}$ on Day 1 and Day 10 in serum iron and TSAT will be calculated with non-compartmental methods using a population approach. Ratio between Day 10 and Day 1 will be calculated.

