3 STUDY ENDPOINTS

3.1 Primary Endpoints

The primary endpoints for the study are pharmacokinetic parameters.

1. Population PK analysis of maltol and maltol glucuronide in plasma from PK samples collected on Day 1 (after first morning dose) and Day 10 (after last morning dose). Parameters to be derived and reported for each Ferric Maltol dose are:
 - C_{max} , $C_{ave(0-6h)}$, $AUC_{(0-6h)}$, and $AUC_{(0-Inf)}$ on Day 1 and Day 10 and ratios of Day 10/Day 1 for these parameters;
 - T_{max} ;
 - Half-life ($t_{1/2}$);
 - Apparent systemic clearance (CL/F); and
 - Apparent volume of distribution (V/F).

Plasma concentrations, including C_{trough} of maltol and maltol glucuronide by time of collection on Day 1 and Day 10 will also be presented.

2. Descriptive and population PK analysis of serum iron and TSAT from PK samples collected on Day 1 and Day 10. Parameters to be derived and reported for each Ferric Maltol dose are:
 - Change from pre-dose (C_{trough}) to maximum post-dose (C_{max}) value for serum iron and TSAT; $C_{ave(0-6h)}$;
 - Pre-dose adjusted Incremental $AUC_{(0-6h)}$ on Day 1 and Day 10 from a population PK analysis approach, and percent change from Day 1 to Day 10; and
 - Apparent systemic clearance (CL/F), apparent volume of distribution (V/F).

Serum iron and TSAT by time of collection on Day 1 and Day 10 will also be presented.

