8.5.1 Basic Model Construction

The maltol and maltol glucuronide concentrations will be analysed simultaneously by means of fitting the compartment models to observed concentration data using a population PK (PPK) approach.

Likewise, the serum iron and TSAT concentrations will be analysed. If the PPK modelling for TSAT is not feasible, population PD (PPD) approach may be performed.

Population PK models will be built using a nonlinear mixed effects modelling technique with NONMEM® software. It is planned that the first order conditional estimation with interaction (FOCEI) method will be used for model development. If this is not feasible (i.e. the model will fail to converge), the first order conditional estimation (FOCE) and the first order (FO) method will be used instead.

Different models will be attempted to fit the PK concentration-time data. The models will include, but are not limited to, one-compartment linear model, one-compartment linear model with first order absorption, two-compartment linear mammillary model, two-compartment linear mammillary model with first order absorption, three-compartment linear model, and three-compartment linear model with first order absorption, linear compartment model with zero order absorption or saturable absorption. Furthermore, a nonlinear compartment model may also be tested, if possible.

For each individual model, model stability will be assessed with the following:

- Model parameter estimates not close to a boundary;
- Shrinkage for interindividual variability terms (ETA) and residual unknown variability (EPS) < 30%;
- Condition number (ratio of the largest to the smallest eigenvalues) < 1000; and
- Correlation less than 0.90 between any two parameter estimates.

For the final PPK model, diagnostic plots will be presented and assessed.

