$R_{AUC0-6h}$	Accumulation ratio based on AUC_{0-6} after first dose and last dose, calculated as $AUC_{0-6(Day10)}/AUC_{0-6(Day1)}$

Pharmacokinetic parameters of maltol and maltol glucuronide will be listed by dose group for each individual subject and summarized by dose group using the following descriptive statistics: n (the number of subjects), arithmetic mean, SD (standard deviation), geometric mean, geometric CV (coefficient of variation), median, minimum and maximum.

Plasma concentration-time courses of maltol/maltol glucuronide on Day 1 and Day 10, including C_{trough} , will be tabulated and graphically displayed per subject and summary statistics will be provided for each dose group for a specific timepoint/day. Plots of mean and geometric mean and plots with combined individual time courses will be provided by dose group.

Actual and/or dose-normalized pharmacokinetic parameters of C_{max} and AUCs will be graphically displayed for maltol and maltol-glucuronide as function of the dose, to explore dose-proportionality.

Serum iron and TSAT:

The following parameters for serum iron and TSAT on Day 1 will be derived for each subject based on the uncorrected and baseline-corrected predicted serum iron concentrations and TSAT, if applicable:

Table 6 Parameters for Serum Iron and TSAT on Day 1

Parameters	Description
C_{\max}	Maximum plasma concentration directly from data
C_{trough}	Pre-dose plasma concentration
Change from C_{trough} to C_{\max}	$C_{\max} - C_{\text{trough}}$
T_{\max}	Time to reach C_{\max}
λ_z	Apparent first-order terminal elimination rate constant
AUC_{0-6h}	Area under the plasma concentration versus time curve from time zero to 6 h using the pre-dose adjusted concentration data
$AUC_{0-\infty}$	Area under the plasma concentration versus time curve from time zero extrapolated to infinity time using the pre-dose adjusted concentration data
CL/F	Apparent clearance calculated as Dose/ $AUC_{0-\infty}$
V_z/F	Apparent volume of distribution (as Dose/ $[\lambda_z * AUC_{0-\infty}]$)

The following parameter for serum iron and TSAT on Day 10 will be derived for each subject based on the uncorrected and baseline-corrected predicted serum iron concentrations and TSAT, if applicable:

Table 7 Parameters for Serum Iron and TSAT on Day 10

Parameters	Description
Tau	The dosing interval for steady-state data tau=12
C_{\max}	Maximum concentration between dose time and dose time + Tau. If not unique, then the first maximum is used.

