C_{trough}	Minimum concentration between dose time and dose time + Tau
Change from C_{trough} to C_{\max}	$C_{\max} - C_{\text{trough}}$
AUC_{0-6h}	Area under the plasma concentration versus time curve from time zero to 6 h using pre-dose adjusted concentration data
$AUC_{0-\tau}$	Area under the plasma concentration versus time curve from time zero to Tau
$C_{\text{ave}(0-6h)}$	Average Steady State Plasma Concentration from 0-6h, calculated as AUC_{0-6h} divided by 6
CL/F	Apparent clearance calculated as Dose/ $AUC_{0-\tau}$
$R_{C_{\max}}$	Accumulation ratio based on maximum concentrations after first dose and last dose, calculated as $C_{\max\text{Day10}}/C_{\max\text{Day1}}$
$R_{AUC0-6h}$	Accumulation ratio based on AUC_{0-6} after first dose and last dose, calculated as $AUC_{0-6(\text{Day10})}/AUC_{0-6(\text{Day1})}$

Pharmacokinetic parameters of serum iron and TSAT will be listed by dose group for each individual subject and summarized by dose group using the following descriptive statistics: n (the number of subjects), arithmetic mean, SD (standard deviation), geometric mean, geometric CV (coefficient of variation), median, minimum and maximum.

Concentration-time courses of serum iron and TSAT on Day 1 and 10, including C_{trough} on Day 1 and 10 will be tabulated and graphically displayed per subject and summary statistics will be provided for each dose group and visit/timepoint. Plots of mean and geometric mean and plots with combined individual time courses will be provided by dose group.

Actual and/or dose-normalized pharmacokinetic parameters of C_{\max} and AUCs will be graphically displayed for serum iron and TSAT as function of the dose, to explore dose-proportionality.

If the PPK model is not feasible for TSAT and PPD model is used for TSAT, the following parameters for TSAT on Days 1 and 10 will be derived for each subject based on the predicted TSAT, if applicable:

Table 8 Parameters for TSAT on Days 1 and 10

Parameters	Description
Baseline	Baseline response value before dosing
R _{max}	Maximum response value
R _{min}	Minimum response value
T _{max}	Time to reach R _{max}
T _{min}	Time to reach R _{min}
AUC _{0-6h}	Area under the effect versus time curve from time zero to 6 h
AUC _{0-24h}	Area under the effect versus time curve from time zero to 24 h
AUC_Above_B	Area under the response curve that is above the baseline
AUC_Below_B	Area that is below the baseline and above the response curve
AUC_Net_B	= AUC_Above_B - AUC_Below_B

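### If TSAT falls back to the PPD analysis, SAP Table 8 does not derive the primary TSAT parameters that SAP 3.1 still requires, and its AUC0-6h is unadjusted under the same name

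*SAP*

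**What the plan says.** SAP 3.1 lists the primary serum iron and TSAT parameters. They are the change from pre-dose to maximum, Cave(0-6h), "Pre-dose adjusted Incremental $AUC_{(0-6h)}$ on Day 1 and Day 10" with its percentage change between those two days, and CL/F and V/F. Protocol 6.3 and 12.2.1 give the same list. Protocol 12.2.1 adds that the adjusted area "will be calculated with non-compartmental methods using a population approach. Ratio between Day 10 and Day 1 will be calculated".

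On the population PK (PPK) route, Tables 6 and 7 of SAP 8.5.4 carry this through. Table 6 defines AUC0-6h "using the pre-dose adjusted concentration data". Table 7 defines its AUC0-6h on pre-dose adjusted data too, and adds a Day 10/Day 1 ratio of AUC0-6h and a Cave(0-6h) equal to AUC0-6h divided by 6.

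SAP 8.5.1 then opens a second route: "If the PPK modelling for TSAT is not feasible, population PD (PPD) approach may be performed". Table 8 gives the parameters for that route on Days 1 and 10. Its AUC0-6h is "Area under the effect versus time curve from time zero to 6 h". Its first baseline-referenced area is "Area under the response curve that is above the baseline", followed by the area below baseline and the net of the two. Baseline is the response before dosing, with no day named. SAP 14 declares no change from the protocol.

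**The concern.** One label, AUC0-6h, stands for two quantities depending on which model works. On the PPK route it measures the rise above the pre-dose value. On the PPD route, read as written, it is the whole area under the TSAT curve, which combines the child's iron status before the dose with uptake from the dose. If pre-dose TSAT moves over nine days of treatment, the unadjusted area moves with it even when uptake does not.

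The other Table 8 rows do not settle this. The net area would match the primary parameter if it ran from 0 to 6 h and used the same day's pre-dose value, but Table 8 states neither. Elsewhere the SAP fixes baseline for the other iron markers as the Day 1 pre-dose value (4.3.1) or the last value before the first dose (9.1), so a programmer could carry Day 1 into the Day 10 calculation.

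TSAT is one of the two primary measures of iron uptake, and Protocol 5.5 says the study data will be used to select the Phase 3 paediatric dose or doses.

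**Working it through.** The documents give no numeric TSAT area to reproduce. The check is a row comparison followed by an illustration.

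**Rows required and rows derived**

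| TSAT parameter in SAP 3.1 | Tables 6 and 7 (PPK) | Table 8 (PPD) |
|---|---|---|
| Change from pre-dose to maximum | Cmax − Ctrough | no row; Rmax and Baseline listed separately |
| Cave(0-6h) | Table 7 only | no row |
| Pre-dose adjusted AUC0-6h | yes | AUC0-6h without adjustment; net area without a window |
| Day 1 to Day 10 change | ratio in Table 7 | no row |
| CL/F, V/F | CL/F in both tables; V/F in Table 6 only | no rows |

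The ratio in Table 7 and the percentage change in SAP 3.1 carry the same information: percentage change = 100 × (ratio − 1).

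**Identity.** With pre-dose value b, total area A and net area N over 0-6 h, A = N + 6b. Table 8 therefore yields the adjusted area as AUC0-6h − 6 × Baseline, provided Baseline is that day's pre-dose value.

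**Illustration.** Protocol 5.4 gives adult 30 mg BID Day 1 means: average peak TSAT 45.6%, and 17.0 above baseline at 6 h, read here as TSAT points. The following are assumed: pre-dose TSAT of 5% to 20%, no rise before 0.5 h, peak at 2.5 h, straight segments.

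A = 0.5b + 2(b + 45.6)/2 + 3.5(45.6 + b + 17.0)/2.

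For b = 10: 5 + 55.6 + 127.05 = 187.65 %·h, so N = 187.65 − 60 = 127.65 %·h.

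Suppose uptake is unchanged and pre-dose TSAT is 5 points higher on Day 10. Then N does not change and A rises by 6 × 5 = 30 %·h.

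| b (%) | A | N | Baseline share 6b/A | Change in A (30/A) | Change in N, same-day baseline | Change in net area if the Day 1 baseline is kept (30/N) |
|---|---|---|---|---|---|---|
| 5 | 171.4 | 141.4 | 18% | +17.5% | 0% | +21.2% |
| 10 | 187.65 | 127.65 | 32% | +16.0% | 0% | +23.5% |
| 15 | 203.9 | 113.9 | 44% | +14.7% | 0% | +26.3% |
| 20 | 220.15 | 100.15 | 55% | +13.6% | 0% | +30.0% |

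**Second curve shape.** With a linear rise from 0 h to the peak at 2.5 h and an exponential decline through the 6 h value, A is 192.6, 209.2 and 225.5 %·h for b = 10, 15 and 20. The same 5-point rise gives +15.6%, +14.3% and +13.3%. The result does not depend much on the shape.

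**When peak level, not the increment, is constant.** On the second shape, with pre-dose TSAT going from 15% to 20% and the peak held at 45.6%, the increment scales by (45.6 − 20)/(45.6 − 15) = 25.6/30.6. N goes from 119.2 to 99.7 %·h (−16.3%), while A goes from 209.2 to 99.7 + 120 = 219.7 %·h (+5.0%).

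**No shift.** If pre-dose TSAT is the same on both days and uptake is unchanged, all the 0-6 h areas show 0%.

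**The case against.** The strongest reply is that nothing has been withdrawn. SAP 3.1 and the protocol still name the TSAT parameters, SAP 14 declares no change, and a derivation table does not override an endpoint section. Most of the absent rows follow from listed ones: change to maximum is Rmax − Baseline, and the adjusted area is AUC0-6h − 6 × Baseline. Same-day pre-dose is also the natural reading of a baseline derived for both days. This stands. A reader might infer that the SAP abandons the primary TSAT endpoint under the fallback, and the documents do not support that. What remains is that Table 8 gives neither the formula nor the baseline day, and attaches the AUC0-6h label to a different quantity.

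Some looseness is not peculiar to Table 8. Tables 6 and 7 also list several areas without a lead, Table 6 has no Cave(0-6h), and Table 7 does not name the day of its adjustment. Nor do the protocol or SAP rank the adjusted area above the other primary TSAT parameters.

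The shifts are assumed. Protocol 5.4 reports adult TSAT on Day 8 as similar to Day 1, which points to a small shift. That limits the likely size but does not remove the mismatch in definition.

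Finally, the fallback is conditional, serum iron keeps its full tables, SAP 8.4 summarises observed TSAT and its change from baseline whichever model is used, and the study is descriptive with no formal sample size calculation. No error rate is affected.

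**Conclusion.** The point holds as a gap in derivation. If the PPD route is used and Table 8 is followed as written, the primary TSAT parameters in SAP 3.1 are not produced, and the row that shares a name with one of them measures something else.

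For unchanged uptake and an assumed 5-point rise in pre-dose TSAT, the unadjusted area would show about +14% to +18% where the required parameter shows 0%. These figures rest on adult 30 mg means and assumed pre-dose values, so they show direction and scale and are not a forecast for children. With no shift there is no discrepancy.

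Two stronger readings are tempting. One is that the Day 10 finding would reverse in sign. That can happen in the constructed case above, but nothing in the documents indicates a shift of that size. The other is that the conclusion could be picked after the data are seen. The parameters are to be listed and summarised rather than selected, there is no Day 10 decision rule, and the endpoint is already named. The supported claim is narrower: before database lock, Table 8 should say which quantity carries the endpoint.

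**What to change.** In SAP Table 8:

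1. Define Baseline as the same day's pre-dose TSAT.
2. Define AUC0-6h as the net area over 0-6 h above that value, equal to the unadjusted area minus 6 × Baseline. Keep the unadjusted area only under a separate label. State the time window for the above-, below- and net-baseline areas.
3. Add Rmax minus Baseline, Cave(0-6h) computed the same way as in Table 7, and the Day 1 to Day 10 percentage change in net AUC0-6h.
4. State that the SAP 3.1 TSAT parameters that can be derived under PPD (change to maximum, Cave(0-6h), net AUC0-6h and its change) remain primary on either route, that CL/F and V/F are not derived under PPD, and that the additional Table 8 rows are supportive. Record this in SAP 14.

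The cost is SAP wording and a few derived variables from the same predicted profiles. No new data, visits or procedures are needed.

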9 SECONDARY ENDPOINT ANALYSIS

9.1 Transferrin, TIBC, UIBC, ferritin and Non-Transferrin Bound Iron (NTBI)

Transferrin, TIBC, UIBC and ferritin will be summarised by dose group and overall by visit/timepoint (Day 1 and Day 10/Pre-dose, 0.5-1h, 1-2h, 2-3h, 3-4h, 4-6h) for the FAS/ITT Population. An additional summary table will present the change from baseline values at each post-baseline visit/timepoint and will include the baseline, visit/timepoint value and change from baseline values for subjects with both baseline and the specified post-baseline values.

Baseline is defined as the last value observed before the first dose.

NTBI will be listed by dose and timepoint for each individual subject; the number of samples considered negative ($<0.2\text{ePLI}$) and positive ($=>0.2\text{ePLI}$) will be summarised by dose group. Individual positive NTBI results ($=>0.2\text{ePLI}$ units) will also be listed separately along with the corresponding serum iron, and TSAT results from those timepoints; plus the plasma C_{\max} , AUC_{0-6h} for maltol and maltol glucuronide on the corresponding study day (Day 1 or Day 10).

A listing of the iron markers and NTBI at each visit/timepoint will be provided for the FAS/ITT Population.

Mean observed values of transferrin, TIBC, UIBC, and ferritin will be plotted on a linear scale against nominal time range by dose group and visit. Combined observed values will be plotted on a linear scale against actual timepoint for each dose group and visit. The change of baseline will be plotted similarly.

Mean observed NTBI will be plotted on a linear scale against nominal time range by dose group and visit. Combined observed NTBI will be plotted on a linear scale against actual timepoint for each dose group and visit.

The concentration plots described above will be prepared based on the actual data, if applicable.

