6.4 SECONDARY ENDPOINTS

1. Descriptive analysis of transferrin, TIBC, UIBC and ferritin concentrations from PK samples collected on Day 1 and Day 10.
2. Descriptive analysis of non-transferrin bound iron (NTBI) concentrations from PK samples collected on Day 1 and Day 10.
3. Descriptive analysis of haemoglobin concentration and absolute reticulocyte count from haematology samples collected at Screening and Day 10.
4. Treatment-emergent Adverse Events (AEs) will be summarised.
5. Treatment-emergent Serious Adverse Events (SAEs) will be summarised.
6. Treatment-emergent Adverse Events leading to premature discontinuation of study drug/PK assessments will be summarised.
7. Clinical laboratory safety blood results at Screening and Day 10 will be summarised.
8. Changes in vital signs and 12-lead ECG will be summarised.
9. Concomitant medications will be summarised.

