4.2 Primary Pharmacokinetic Measurements and Variables

4.2.1 PK blood sampling

On study days 1 and 10, all subjects were to have baseline (pre-dose) PK blood samples collected immediately prior to Ferric Maltol dosing (0h). Subjects were then to have further PK blood samples collected at two additional times between 0.5h and 6h after dosing on Days 1 and 10; within each Ferric Maltol dose group (7.8 mg, 16.6 mg or 30 mg BID), the post-dose PK sample time collection windows were 0.5-1h, 1.0-2.0h, 2.0-3.0h, 3.0-4.0h and 4.0-6.0h. The 12 subjects within each Ferric Maltol dose group were assigned to the required post-dose PK blood sampling schedule in sequential order at the time of randomisation, based on current subject enrolment across all study sites. Table 3 details the sparse PK blood sample schedule.

Table 3 Sparse PK Blood Sampling Schedule

	PK Sample Schedule			
	Group 1 (N = 3/12)	Group 2 (N = 3/12)	Group 3 (N = 3/12)	Group 4 (N = 3/12)
Pre-dose (0h)	X	X	X	X
0.5 – 1h	X	X		
1.0 – 2.0h	X		X	
2.0 – 3.0h		X		X
3.0 – 4.0h			X	
4.0 – 6.0h				X

For each individual subject, the post-dose PK blood sampling schedule was to be the same on Day 1 and Day 10. Post-dose samples for each subject were to be collected within the allocated time-windows (e.g. between 0.5-1h or 1-2h); the exact time of the sample collection was to be recorded in the eCRF. For those subjects in PK Sample Schedule Group 1 (see Table 3), the PK blood samples for the 0.5-1h timepoint window were to be taken at 30 minutes prior to the PK blood samples for the 1-2h timepoint window on Day 1 and Day 10, to provide an adequate spread of actual sampling times for the population PK analysis.

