4.3 Secondary Endpoint Measurements and Variables

4.3.1 Iron Markers and Non-Transferrin Bound Iron (NTBI)

Iron markers include transferrin, total and unsaturated iron binding capacity (TIBC and UIBC) and ferritin. Iron markers and NTBI were to be collected on Day 1 and Day 10, pre-dose and post-dose according to the PK Sample Schedule Group that the subject was assigned to.

The following list of iron markers and NTBI will be available from the standard export from MRL:

- Transferrin (units) g/l
- TIBC (units) $\mu\text{mol/L}$
- UIBC (units) $\mu\text{mol/L}$
- Ferritin ($\mu\text{g/L}$) $\mu\text{g/L}$
- NTBI (units) <0.2 eLPI unit =negative, ≥0.2 eLPI unit=positive

The data transport files from MRL will contain iron markers in the standard reporting units of the reporting laboratory and in SI units. All iron markers will be converted to and reported using units indicated in parenthesis above.

Baseline for iron markers and NTBI is defined as the pre-dose value observed at the Day 1 Visit. Change from baseline to each post-baseline visit/timepoint will be derived for each parameter as visit/timepoint value minus baseline.

NTBI results will be available from the data export from Afferix Ltd.

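### The only planned NTBI summary table counts samples, not children, and makes no pre-dose/post-dose split, so it cannot show how many children became positive after dosing

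*SAP*

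**What the plan says.** Protocol 6.4 lists as a secondary endpoint: "Descriptive analysis of non-transferrin bound iron (NTBI) concentrations from PK samples collected on Day 1 and Day 10". SAP 4.3.1 sets the cut-off (0.2 eLPI unit or more is positive) and the sampling: "Iron markers and NTBI were to be collected on Day 1 and Day 10, pre-dose and post-dose according to the PK Sample Schedule Group" to which the child was assigned. It also fixes a reference point: "Baseline for iron markers and NTBI is defined as the pre-dose value observed at the Day 1 Visit". It then says that change from baseline will be derived for each parameter.

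SAP 9.1 gives the output. The NTBI sentence begins "NTBI will be listed by dose and timepoint for each individual subject; the number of samples considered negative" and goes on to say that these negative and positive counts "will be summarised by dose group. Individual positive NTBI results" are then to be listed separately, with the matching serum iron and TSAT and that day's maltol exposure. The same section says of the other markers: "Transferrin, TIBC, UIBC and ferritin will be summarised by dose group and overall by visit/timepoint", and adds a change-from-baseline table for them.

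Other NTBI outputs in SAP 9.1 are a listing by visit and timepoint, a plot of mean NTBI against nominal time by dose group and visit, and a plot of all observed values against actual time.

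**The concern.** A reader comparing doses needs to know how many children were negative before the first dose and positive afterwards. The planned table gives a number of samples. It treats a sample drawn before any drug like one drawn two hours after the tenth morning dose, and six positives from one child like one positive from each of six children. The baseline in SAP 4.3.1 feeds no NTBI output named in SAP 9.1; even the change-from-baseline plots follow the other markers and not NTBI.

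The SAP handles adverse events differently. SAP 10.1 counts subjects, counts repeat episodes of the same term once, and separates treatment-emergent events.

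At stake is one descriptive table for a named secondary endpoint, in a study whose data are to be used to select doses for the Phase 3 paediatric trial (Protocol 5.5).

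**Working it through.** The documents give no NTBI rate, power or sample-size figure to reproduce. The sample counts follow from the schedule; the positivity rates below are assumptions.

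**Inputs**
- 12 children per dose group (SAP 13).
- On each of Days 1 and 10, every child has one pre-dose sample, then "further PK blood samples collected at two additional times between 0.5h and 6h after dosing on Days 1 and 10" (SAP 4.2.1).
- NTBI is assayed at every sampling timepoint, pre-dose included (Protocol 10.7.2).

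**Planned samples per dose group**
- Total: 12 × 2 × (1 + 2) = 72.
- Pre-dose: 12 × 2 × 1 = 24 (33.3%). Of these, 12 (16.7%) precede any drug, and the 12 on Day 10 follow nine days of dosing.
- Post-dose: 12 × 2 × 2 = 48 (66.7%).
- By window over both days: 24 at 0 h, 12 at 0.5–1 h, 12 at 1–2 h, 12 at 2–3 h, 6 at 3–4 h, 6 at 4–6 h; sum 72. On one day, each post-dose window holds 6 or 3 children.

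**Unit of count**
- Each child gives up to 6 samples, so 12 positives need at least 12/6 = 2 children and at most 12. If all 12 are post-dose (up to 4 per child), the minimum is 12/4 = 3.
- One child positive at every sample, including before the first dose, adds 6/72 = 8.3% to that dose group.

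**Effect on a percentage, if one is shown**

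Let q be the post-dose and p0 the pre-dose positivity rate. Pooled rate = (48q + 24p0)/72.
- p0 = 0: q = 5% reads 3.3%; 10% reads 6.7%; 25% reads 16.7%; 50% reads 33.3%. The factor is 48/72 = 2/3.
- q = 25%: p0 = 5% reads 18.3%; p0 = 10% reads 20.0%.
- p0 = q = 10%: reads 10.0%, no dilution.
- q = 5%, p0 = 10%: reads 6.7%, above the post-dose rate.

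**Difference between two doses.** It shrinks to 2/3 if neither pre-dose set carries a dose effect. It shrinks to 60/72 = 5/6 if only the Day 1 pre-dose samples are free of one and the Day 10 pre-dose samples show the same difference as the post-dose samples.

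**The case against.** The strongest reply is that most of the information is already planned. The NTBI plots separate times by dose group and visit, every positive is listed with its matching serum iron and TSAT, and with 12 children per group a reader can trace each child. This stands: a reader might infer that the report will hide the timing, and the documents do not support that. They also do not show that the pooled count is the figure that will be quoted. But a mean plot does not count children crossing 0.2, and a listing leaves the reader to build the summary.

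The pooling is inferred: SAP 9.1 does not state it, and no table shell is available. The contrast with the neighbouring sentence on the other markers makes it the natural reading. A timepoint split would still leave the sample as the unit.

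A reader might infer that pooling always dilutes. It does not. The raw positive count is unaffected, and a percentage (which SAP 6.2 would allow) is diluted only if pre-dose positivity is lower than post-dose. Day 10 pre-dose samples are not drug-free. If all pre-dose samples are negative, the ratio between doses is preserved, because the sampling plan is the same at each dose.

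A reader might also infer that many children are never sampled near the iron peak. Protocol 5.4 puts the adult serum iron and TSAT maxima between 1.5 and 3 h. The 1–2 h and 2–3 h windows together hold 24 samples per dose group, from all 12 children. The documents give no time course for NTBI itself.

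Nor do they support treating NTBI as the study's sole evidence on saturation of binding capacity; TSAT and UIBC are also measured and reported.

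**Conclusion.** The point holds for the summary table. As worded, it cannot separate positivity present before treatment from positivity that appears after dosing, or one child from several, and no other planned summary supplies the number of children who became positive. SAP 4.3.1 defines and derives what is needed; SAP 9.1 does not tabulate it.

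The size is modest. The sample counts assume complete planned sampling in 12 children per group. The two-thirds figure also assumes that a percentage is shown and that all pre-dose samples are negative. The defect is confined to one descriptive table of a secondary endpoint, the underlying data remain in the listings and plots, and the primary PK analysis is untouched. The change is worth making because it is cheap and gives a figure that can be compared between doses.

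**What to change.** In SAP 9.1, replace the sample count with a table of NTBI positive/negative by dose group, visit and pre-dose/post-dose, with the number of children sampled as the denominator. A further split by time window is optional, since those cells hold only 3 or 6 children.

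Add the number and percentage of children negative at Day 1 pre-dose who have at least one later positive, split into Day 1 post-dose, Day 10 pre-dose and Day 10 post-dose (a child may appear in more than one). The denominator is 12 per group less any child positive at baseline. Show children positive at Day 1 pre-dose on a separate line, and likewise any child with no Day 1 pre-dose result: NTBI is not among the screening iron markers, so there is no other baseline value.

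The cost is a change of SAP wording and one revised table from data already being collected. The drawback is small cells, which should be read as counts. The existing listings and plots stay as they are.
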